Patients diagnosed with diabetic foot will have significant changes after hyperbaric treatment such as increased gene expression in the antioxidant response and decreased gene expression in the inflammatory response.

General Objective:

To evaluate gene expression changes in inflammation and oxidative stress in diabetic foot patients treated with hyperbaric oxygen.

Specific objectives:

□ To evaluate the clinical and biochemical characteristics of the included patients according to sex.

□ To evaluate the gene expression of SOD, CAT, GPX, GRd, NLRP3, IL-1b, Casp-1, IL-4, IL-6, IL-10 and IL-13 in the basal state, at 12 and 30 sessions of treatment in the hyperbaric chamber.

Methodology:

Type of study: quasi-experimental, longitudinal, prolective, analytical study.

Characteristics of the population:

Women and men older than 18 years, with Diabetes type 2, residents of the CDMX, with diabetic foot with hyperbaric treatment, attended at the hospital of specialties in diabetes, secretary of health, accepted and signed the informed consent form.

Selection criteria:

Men and women with diabetic foot and hyperbaric treatment. Ages 30-60 years. Signed informed consent form.

Exclusion:

Patients with diabetic foot without presence of dermatologic lesions.

Elimination:

Patients who decided to abandon the protocol. Incomplete data for any variable.

Sample size:

15 patients with diabetic foot.

Operationalization of variables:

Variable	Туре	Measuring unit
Age	Quantitative	Years
Sex	Qualitative	Male/ female
Systemic blood	Quantitative	Milimeters of mercury
pressure		
Waist	Quantitative	Centimeters
Dislipidemias	Qualitative	Positive or negative
Anaemia	Qualitative	Positive or negative
Tabaquism	Qualitative	Positive or negative
Charcot's foot	Qualitative	Positive or negative
Chronic kidney	Qualitative	Positive or negative
disease by CKD-		
EPI I-III		
Insuficiencia	Qualitative	Positive or negative
venosa periférica		
Glucosa en sangre	Quantitative	milligrams/ deciliters
Colesterol	Quantitative	milligrams/ deciliters
Triglicéridos	Quantitative	milligrams/ deciliters
Basal glycosylated	Quantitative	Percentage
hemoglobin basal		
Creatinina	Quantitative	milligrams/ deciliters
Tasa de filtrado	Quantitative	milliliters/ square meter of body surface area
glomerular		
glycosylated	Quantitative	Percentage

hemoglobin at 3		
months		
Wagner's	Qualitative	Wagner
classification for		Grade 0: Absence of ulcers in a high-risk foot.

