- 6. The gRT-PCR technique to determine relative expression, a "master mix" (10 μ L) was prepared in microtubes for the LightCycler nano (Roche Diagnostics), the mix was composed of 100 nM forward oligonucleotides, 100 nM reverse oligonucleotides, 100 nM hydrolysis probe (Human Universal Probe Library, Roche Diagnostics), 2 µL TagMan master (Tag-polymerase), 0. 5 U LightCycler Uracil-DNA glycosylase, and 2 µL of DNAc (500 ng). The mixture was subjected to different temperature changes in the LightCycler Nano Real-Time PCR System (Roche Diagnostics) under the following conditions: initial incubation (denaturation) at 95 °C for 10 minutes, followed by 45 cycles of: denaturation (95 °C for 10 seconds), allylation of oligos to cDNA (60 °C for 30 seconds), and extension (copying) of the cDNA strand (72 °C for 1 minute). The specific sequences used to design the oligonucleotides used in gRT-PCR were ProbeFinder: designed using the online software https://lifescience.roche.com/shop/en/us/overviews/brand/universal-probelibrary.
- Relative RNAm expression of genes was normalized to the relative expression levels of the housekeeping gene (18s). Relative quantification (normalization) of gene expression was determined using the 2-ΔΔΔCT method.

Statistical analysis

In the analysis, qualitative variables are presented in frequencies and percentages, compared with the Chi-square test; quantitative variables according to the Shapiro-Wilk normality test, normally distributed variables are presented in means and standard deviation, compared with Student's t-test, those related with ANOVA test; quantitative variables of free distribution are presented in medians and interquartile ranges, compared with Mann Whitney U-test, those related with Kruskall-Wallis test. Data analysis was carried out with SPSS version 23, Graph Pad Prisma. A value p<0.05 was taken as statistical significance, 95% confidence interval (95%CI).

Ethical aspects:

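### The plan has no rule for a qRT-PCR reaction that gives no CT by cycle 45; read literally, its elimination rule would drop the whole patient for an informative low result

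*Combined protocol and SAP*

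**What the plan says.** - **Assay (Procedure, step 6).** After an initial denaturation, amplification is "followed by 45 cycles of: denaturation", annealing and extension. No further cycles are run.
- **Quantification (paragraph after step 6).** "Relative quantification (normalization) of gene expression was determined using the" comparative CT method, with 18s as the reference gene. Every expression value therefore needs a CT for the target and a CT for 18s.
- **Genes and visits (Specific objectives).** The genes are "SOD, CAT, GPX, GRd, NLRP3, IL-1b, Casp-1, IL-4, IL-6, IL-10 and IL-13", measured "in the basal state, at 12 and 30 sessions of treatment in the hyperbaric chamber".
- **Elimination (Methodology).** Besides patients who abandon the protocol, the plan eliminates those with "Incomplete data for any variable". The table of variables lists gene expression as a variable.
- **Hypothesis.** It predicts "decreased gene expression in the inflammatory response", alongside a rise in antioxidant expression.
- **Sample size.** "15 patients with diabetic foot", without derivation.

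The document mentions no detection limit, CT cut-off, repeat run or substituted value. The Statistical analysis section has no missing-data method and no sensitivity analysis.

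**The concern.** A reaction that does not amplify by cycle 45 has no CT, so its relative expression cannot be computed. If the reaction itself worked, the result is still informative: the transcript is too scarce to detect. The plan has no category for this. Its only instruction for an absent value is to eliminate the patient, so a literal reader would discard a very low measurement as though it had never been made.

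Two things are at stake. The first is patients: a non-detect in any one gene at any one visit would remove all that patient's data, and the study has only 15. The second is bias. If inflammatory transcripts fall as hypothesised, non-detects become more common at sessions 12 and 30 than at baseline. Removal then depends on the outcome being studied.

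**Working it through.** **Inputs from the document.** 15 patients; 11 genes; 3 time points; 45 cycles; elimination for any incomplete variable. The sample size of 15 cannot be reproduced, because no effect size, SD, power or formula is given. Everything below on CT levels, copy numbers and non-detect rates is assumed.

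**1. Patients kept, if a non-detect triggers elimination.** Results per patient: 11 x 3 = 33. With a non-detect rate q per result, treated as independent, the expected number kept is 15 x (1 - q)^33.

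| q | (1 - q)^33 | Expected kept of 15 |
|---|---|---|
| 0.5% | 0.848 | 12.7 |
| 1% | 0.718 | 10.8 |
| 2% | 0.513 | 7.7 |
| 5% | 0.184 | 2.8 |

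Non-detects clustered in the same patients or genes would remove fewer patients for the same q.

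**2. Direction and size of bias, CT model.** One gene, 400,000 simulated patients. Baseline CT has SD 2. The CT change has SD 1.5, with mean +1 cycle at session 30 (a fall in expression) and half of that at session 12. A patient is removed if any of the three CTs reaches 45. The true change is 1.00.

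| Mean baseline CT | Removed | Estimate after elimination | Estimate if CT is set to 45 and patient kept |
|---|---|---|---|
| 30 | 0.0% | 1.00 | 1.00 |
| 38 | 1.2% | 0.98 | 0.99 |
| 41 | 15.7% | 0.84 | 0.88 |
| 43 | 43.9% | 0.61 | 0.58 |

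In this model later CTs vary more than baseline CTs (SD = square root of (2^2 + 1.5^2) = 2.5 against 2). That contributes to the shift: with no true change, the estimate at mean CT 43 is -0.22.

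**3. Check with equal SDs, and by visit of the non-detect.** Baseline and final CT only, SD 2 each, correlation 0 to 0.9, true change 1.00.

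| Patients removed for a non-detect at | Mean CT 41 | Mean CT 43 |
|---|---|---|
| final visit only | 0.72 to 0.97 | -0.02 to 0.90 |
| baseline only | 1.01 to 1.11 | 1.06 to 1.57 |
| either | 0.83 to 0.98 | 0.55 to 0.92 |

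Baseline removal pushes the other way, but the net effect is still understatement.

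**4. Copy-number model.** Log2 baseline copies have SD 1 around the log2 of the median. The log2 change at session 30 has mean -1 and SD 0.8, with half of it at session 12. Counts are Poisson, and a patient is kept if all three counts exceed zero.

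| Median baseline copies | Kept | Estimate (true -1.00) |
|---|---|---|
| 3 | 60.0% | -0.63 |
| 10 | 92.2% | -0.93 |
| 20 | 98.1% | -1.01 |

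At 3 copies the removed 40% have a true mean change of -1.264. The kept patients' true mean is therefore (-1.00 + 0.40 x 1.264) / 0.60 = -0.82. Of the total shift of 0.37, losing patients explains 1.00 - 0.82 = 0.18. The other 0.19 is counting noise in the retained patients, whose counts are conditioned to be above zero.

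**5. Does dropping the any-variable rule cure it?** No. Using every patient with a baseline and a session-30 value gives -0.61 at 3 copies and -0.94 at 10.

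**The case against.** Several objections are sound and limit the point.

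- **No rule says that a missing CT is incomplete data.** A reader might infer that the plan removes such patients as a stated practice. It does not say so. The laboratory could set CT to 45 or record zero expression. What stands is that elimination is the only rule given for an absent value, and that setting CT to 45 also understates the fall in step 2.
- **Those removed are not simply the patients whose genes fall most.** That stronger reading is tempting, but removal follows low level at any visit. In the 3-copy scenario it correlates -0.53 with baseline level and -0.27 with steepness of fall. It takes 77% of the lowest-baseline quartile and 58% of the steepest-fall quartile, so 42% of the steepest fallers stay.
- **The size is not known.** The documents give no CT, copy number, SD or effect size. Material bias needs a gene already near the detection limit, and nothing shows that any of the 11 is. The -0.63 in step 4 should not be read as a prediction.
- **Correcting the elimination rule would cover part of this.** It would stop the loss of whole patients, but step 5 shows that the bias would remain.
- **A simple remedy can mislead.** A valid 18s CT does not prove that the separate target reaction worked; coding a failed target reaction as low expression would create false decreases in the hypothesised direction. Nor is a non-detect always the lowest value after normalisation. For illustration, a non-detect with 18s CT 15 has delta-CT above 45 - 15 = 30, while a detected sample at CT 44 with 18s CT 10 has delta-CT 34. The fix below allows for both.

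**Conclusion.** The point holds as a gap in the plan with a conditional consequence. The 45-cycle cap, expression computed only from CT, and elimination for any incomplete variable are all in the text, and no non-detect rule is. Followed literally, they remove a patient's 11 genes because of one below-detection result. The expected number kept is 10.8 of 15 at an assumed independent rate of 1%, and 7.7 at 2%.

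If inflammatory expression truly falls and the gene lies near the detection limit, the net bias was towards understating the fall in all the models run. At a mean baseline CT of 41 a true 1.00-cycle change is estimated at 0.83 to 0.98; at 43, at 0.55 to 0.92. At CT 38 the effect is negligible (0.98), and at CT 30 it is nil. Which case applies cannot be judged from the documents. The evidence therefore does not show that the study's result will be understated, only that the plan leaves it exposed. The handling should be settled before the CT results are examined, because otherwise the choice can follow the results.

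**What to change.** Add to the Procedure and Statistical analysis sections, with a cross-reference from Elimination:

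1. A target with no CT by cycle 45, in a sample with a valid 18s CT and valid reaction controls for that target, is a below-detection result. It is not incomplete data, and the patient is kept.
2. The value is treated as left-censored expression: delta-CT is above 45 minus that sample's own 18s CT. In a rank analysis it is tied at the lowest rank only where that bound supports doing so.
3. The comparison across visits is paired within patient. The tests named now include Mann-Whitney and Kruskal-Wallis, which do not use the pairing, so a paired method has to be specified.
4. A technical failure of either the 18s or the target reaction is missing.
5. Non-detects are reported by gene and visit.

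In the 3-copy scenario, keeping patients with non-detects coded low gave a median change of -1.0, the true value. The cost is a few sentences, a little more analysis work, and less precise fold changes for genes near the detection limit. If non-detects prove rare, the rule changes almost nothing.

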diabetic feet		Grade 1: Superficial ulcer involving the full
		thickness of the skin but no underlying
		tissues.
		Grade 2: Deep ulcer, penetrating to ligaments
		and muscles but not involving bone or
		abscess formation.
		Grade 3: Deep ulcer with cellulitis or abscess
		formation, almost always with osteomyelitis.
		Grade 4: Localized gangrene.
		Grade 5: Extensive gangrene involving the
		entire foot.
Gene expression	Qualitative	International units
SOD, CAT, GPX,		
GRd, NLRP3, IL-		
1b, Casp-1, IL-4,		
IL-6, IL-10 e IL-13.		

Procedure:

- 1. Patients attended at the diabetic foot clinic in the CDMX were invited to participate. 2.
- 2. An informed consent process was carried out with the patient's signature to agree to participate in the study.
- 3. Questions were asked about their personal pathological and non-pathological history.
- 4. Three tubes of blood samples were taken for determination of blood biometry, urea, creatinine, cholesterol, triglycerides, glycosylated hemoglobin. A 4 ml tube

with EDTA was taken to measure the gene expression of SOD, CAT, GPX, GRd, NLRP3, NLRP3, IL-1b, Casp-1, IL-4, IL-6, IL-10 and IL-13.

- 5. Complementary DNA (cDNA) synthesis was carried out following the instructions of the Transcriptor First Strand cDNA Synthesis kit (Roche Diagnostics), using a mixture of random hexamer primers, nitrogenous bases (A, T, G and C), reaction buffer, RNase inhibitor and Reveso Transcriptase enzyme. The retrotranscription reaction was carried out in a thermocycler (Eppendorf Mastercycler) programmed at an initial temperature of 25°C for 15 minutes, 45°C for 60 minutes and 72°C for 15 minutes.

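### Gene expression, the main outcome, is typed as qualitative and so routed to Chi-square although it is a continuous relative quantity; once that is corrected, the scale to be tested is still not stated

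*Combined protocol and SAP*

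**What the plan says.** The General Objective is "To evaluate gene expression changes in inflammation and oxidative stress in diabetic foot patients treated with hyperbaric oxygen". The Hypothesis is directional: "increased gene expression in the antioxidant response and decreased gene expression in the inflammatory response". The second specific objective sets three measurements per patient, "in the basal state, at 12 and 30 sessions of treatment in the hyperbaric chamber". The sample is 15 patients.

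The row for gene expression in Operationalization of variables covers 11 analytes. It gives the type as qualitative and the unit as "International units".

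Under Statistical analysis, "qualitative variables are presented in frequencies and percentages, compared with the Chi-square test". The other route is "quantitative variables according to the Shapiro-Wilk normality test": a pass leads to means, SDs, t-test and, for related variables, ANOVA. A failure leads to medians, interquartile ranges, Mann-Whitney and, for related variables, Kruskal-Wallis. Gene expression is not mentioned as an exception to either route.

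The Procedure says "Relative quantification (normalization) of gene expression was determined using the" 2^-delta-delta-CT type method, with 18s as the housekeeping gene.

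**The concern.** The row that assigns the main outcome to an analysis contradicts the way that outcome is measured. Relative quantification by PCR gives a continuous ratio. It has no unit, so international units do not apply, and it has no categories, so a table of frequencies cannot be formed from it.

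Correcting the type is not enough. 18s fixes the first delta only. The document does not name the calibrator for the second delta (the patient's own basal sample or a group basal mean), nor the scale that enters the normality test and the comparisons. The plan lets Shapiro-Wilk choose the test, and fold change is skewed whenever delta-CT is roughly symmetric. An analyst left to pick the scale after seeing the data therefore also has a hand in picking the test, gene by gene, for 11 genes.

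**Working it through.** **1. Is the qualitative typing intended?** Eight other rows are typed qualitative: sex, six positive/negative items and Wagner grade. Each lists its categories. The gene expression row lists none, and no cut-off appears elsewhere. The hypothesis speaks of increase and decrease. A slip is the likely explanation, but no other text overrides the row.

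**2. The rule taken literally.** With 15 patients at 3 times and 45 distinct values, the table is 3 x 45 with one observation per column. Each expected count is 15/45 = 1/3. Each column contributes (1 - 1/3)^2/(1/3) + 2 x (1/3)^2/(1/3) = 4/3 + 2/3 = 2. The total is 45 x 2 = 90 on 2 x 44 = 88 df, p = 0.42, whatever the treatment does. This shows only that the rule cannot address the hypothesis.

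**3. The scale and the normality test.** The documents give no CT variability, so these inputs are assumptions: delta-CT normal, n = 15, a two-fold fall by session 30 with half of it (in cycles) by session 12, and SDs over a range. The percentage of simulated trials passing Shapiro-Wilk at all three times is:

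| Between / within-patient SD (cycles) | Delta-CT | Group-scaled fold change |
|---|---|---|
| 0.3 / 0.3 | about 86% | about 57% |
| 0.5 / 0.5 | about 86% | about 26-27% |
| 1 / 0.5 | about 86% | about 9% |
| 1 / 1 | about 86% | about 1% |

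The delta-CT column follows from the normality assumption (0.95^3 = 0.857) and is not evidence about real CT data.

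**4. Own-basal scaling.** Every basal value is then 1 (2^0), so Shapiro-Wilk cannot be computed at basal. The between-patient SD cancels; only the within-patient SD matters.
- Type I error at nominal 5%: about 6.5-7% with Kruskal-Wallis. With repeated-measures ANOVA it is about 7% at within-patient SD 0.5 and about 10% at SD 1, against 5% on delta-CT.
- Arithmetic mean: the difference of two delta-CT values has variance 2 x SD^2, so the expected fold is the true fold x exp((ln 2)^2 x SD^2). At SD 0.5 / 1 / 1.4 the factor is 1.13 / 1.62 / 2.56. A true halving then averages 0.56 / 0.81 / 1.28. Medians and geometric means do not carry this bias.

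**5. Power.** With between-patient SD 1 and within-patient SD 0.5 / 1 / 1.4:
- Unpaired tests chosen by Shapiro-Wilk, delta-CT v group-scaled fold change: 52% v 50%, 28% v 26%, 19% v 18%.
- Own-basal fold change passes Shapiro-Wilk at sessions 12 and 30 in about 41% / 4% / 0.3% of trials, so the plan usually leads to Kruskal-Wallis. Its power is then 99% / 56-58% / 35-36%, against 99.8% / 64% / 36% for repeated-measures ANOVA on delta-CT.

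**The case against.** The strongest reply is that this is a table slip in a roughly translated text. The PCR method and the directional hypothesis make the quantitative reading plain, and nobody would cross-tabulate 45 distinct values. That is fair as to intent. It does not supply the missing scale, and the written rule for the main outcome remains wrong.

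A second reply is that naming a delta-delta-CT type method already implies fold change. It does suggest what will be reported. It does not say what will be tested, or against which calibrator.

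A third concerns the size of the harm, and most of it stands. A reader might infer a large loss of power, since repeated-measures ANOVA run directly on own-basal fold change would have only 20% power at within-patient SD 1 and 8% at SD 1.4. The plan's own normality rule would usually prevent that analysis. Kruskal-Wallis also gives the same result on delta-CT and on group-scaled fold change, because the ranks are unchanged apart from direction. A gap does appear if normal data go to repeated-measures ANOVA and the rest to Kruskal-Wallis (59% v 27% at SDs 1 / 1). It arises because pairing is lost on the second route, which is a separate matter.

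Finally, the upward bias needs arithmetic means, whereas the plan prescribes medians for non-normal data. The bias therefore bites only where means are reported.

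**Conclusion.** The point holds as a contradiction in the plan plus an omission, and should be fixed. The type and unit of the main outcome are wrong as written, the Chi-square rule cannot test the hypothesis, and the tested scale is not stated. These conclusions rest on the text alone.

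The consequences are conditional. Under normal CT values and the assumed SDs, the scale can decide which test is used: 57% down to 1% of trials pass on group-scaled fold change, against about 86% on delta-CT. Own-basal scaling inflates type I error modestly, to about 6.5% with Kruskal-Wallis and 7-10% with repeated-measures ANOVA, and biases an arithmetic mean fold upward.

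Three stronger readings are not supported. The documents do not show that Chi-square was applied to gene expression. Loss of power is not a main consequence. The unnamed calibrator does not undermine a within-patient test on delta-CT, because it cancels there; naming it affects reporting only.

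**What to change.** Change the table row to: *Gene expression - Quantitative (continuous) - relative expression, no unit.*

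Add to Statistical analysis: *For gene expression, Shapiro-Wilk and the within-patient comparison of basal, 12 and 30 sessions use delta-CT (target CT minus 18s CT). In place of the mean/SD or median/IQR rule, results are reported as geometric mean fold change from the patient's own basal sample, 2^-(mean delta-delta-CT), with back-transformed 95% CI.*

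The second sentence is needed because the present reporting rule does not provide for geometric means. If the analysis has already been run, the text should state which scale and calibrator were used.

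The cost is one table row, a short addition on scale and reporting, and relabelled graphs. Delta-CT is already computed on the way to the relative quantity, so no new samples or assays are needed.

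### With 15 patients the expected-count condition of the Chi-square test can never be met in a 2x2 table by sex; one exact test should be named instead

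*Combined protocol and SAP*

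**What the plan says.** The Statistical analysis section names a single test for all categorical data: "qualitative variables are presented in frequencies and percentages, compared with the Chi-square test". The threshold is stated as "A value p<0.05 was taken as statistical significance". The section does not say whether a continuity correction applies or what happens when counts are small. The software statement, "Data analysis was carried out with SPSS version 23, Graph Pad Prisma", does not settle which form of the test is meant.

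The Sample size entry reads "15 patients with diabetic foot". The first specific objective is "To evaluate the clinical and biochemical characteristics of the included patients according to sex". There is one treated group, so sex is the only grouping the plan names.

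In the table of variables, six characteristics are coded "Positive or negative": dyslipidaemia, anaemia, smoking, Charcot's foot, chronic kidney disease and venous insufficiency. Wagner grade has six levels. The elimination criteria include "Incomplete data for any variable", so the analysed number may be below 15.

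**The concern.** The Chi-square test takes its p-value from a large-sample distribution. The usual condition for relying on it is an expected count of at least 5 in each cell. If 15 patients can never meet that condition, the plan has named a method whose standard justification is absent in every table it will produce.

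At stake is whether a listed objective reports a sex difference as significant at 0.05 when an exact calculation from the same counts does not. Because the form of the test is left open, the same table could also be significant or not depending on a software setting.

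**Working it through.** **Inputs.** N = 15 (Sample size); Chi-square test and threshold 0.05 (Statistical analysis); binary characteristics compared by sex (table of variables, Specific objectives). The sex split and the prevalence of each characteristic are not given. Splits from 1/14 to 7/8 and common prevalences from 0.01 to 0.99 are therefore assumptions. The sample size has no calculation behind it, so there is no figure of the plan's own to reproduce.

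**Step 1: expected counts.** The smallest expected count is (smaller row total x smaller column total) / N. With N = 15 neither smaller total can exceed 7, so the maximum is 7 x 7 / 15 = 3.27. Losing patients does not help: the first N at which all four cells can reach 5 is 20 (10 x 10 / 20 = 5).

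**Step 2: two tables by hand.** For a of m in one sex and b of n in the other, the uncorrected statistic is X² = N(ad − bc)² / (product of the four margins), where c and d here are the negatives in the first and second sex, so that the cross-product is a(n − b) − b(m − a).

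- 3/7 versus 0/8: X² = 15 x (3 x 8 − 0 x 4)² / (7 x 8 x 3 x 12) = 8640 / 2016 = 4.29, p = 0.038. Fisher: C(7,3) / C(15,3) = 35 / 455 = 0.077. The opposite extreme, 56 / 455, is more probable and is not added. With continuity correction, p = 0.155.
- 1/3 versus 0/12: X² = 15 x (1 x 12 − 0 x 2)² / (3 x 12 x 1 x 14) = 2160 / 504 = 4.29, p = 0.038. Fisher: 3 / 15 = 0.20. With continuity correction, p = 0.44.

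**Step 3: all tables.** Every 2x2 table with N = 15 and non-zero margins was enumerated (378 tables). The type I error is the exact rejection probability when both sexes share one prevalence, maximised over the prevalence grid.

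| Sex split | Significant, uncorrected Chi-square | Of these, not significant by Fisher | Max type I error, Chi-square | Max type I error, Fisher |
|---|---|---|---|---|
| 7/8 | 24 | 4 | 0.047 | 0.035 |
| 6/9 | 22 | 2 | 0.043 | 0.035 |
| 5/10 | 22 | 6 | 0.050 | 0.028 |
| 4/11 | 18 | 6 | 0.051 | 0.017 |
| 3/12 | 16 | 6 | 0.089 | 0.019 |
| 2/13 | 10 | 6 | 0.056 | 0.010 |
| 1/14 | 6 | 6 | 0.097 | 0 |

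In total, 118 tables are significant by uncorrected Chi-square and 82 by Fisher. The 36 that differ all go the same way. For splits 4/11 to 7/8 the totals are 86 and 68, a difference of 18. With continuity correction 62 tables are significant, and Fisher agrees with all of them.

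**Step 4: where the inflation lies.** At 3/12 the uncorrected error is 0.087 at a prevalence of 0.1, 0.061 at 0.2, 0.045 at 0.3 and 0.051 at 0.5. It is a problem of rare (or nearly universal) characteristics combined with an uneven split.

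**The case against.** The strongest reply is that an expected count below 5 is a rule of thumb and does not by itself show an inflated error rate. For splits from 4/11 to 7/8 the uncorrected test holds its level almost exactly, and much of the gap there is Fisher's conservatism. Other small-sample tests can side with the Chi-square result: for 3/7 versus 0/8, mid-p gives 0.038 and Barnard's unconditional exact test 0.046; for 2/5 versus 0/10 (Chi-square 0.032, Fisher 0.095), they give 0.048 and 0.042. Only in the 1/3 versus 0/12 table do they side with Fisher (0.10 and 0.089). If the analyst applies the continuity correction, the discordance disappears. All of this stands.

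Four stronger readings are therefore tempting but unsupported:

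- *The test always gives wrong p-values or false sex differences.* It disagrees with Fisher in 36 of 118 significant tables if uncorrected, and in none in this direction if corrected.
- *The false-positive rate is 20%.* That figure (3 / 15) holds only given a 3/12 split and exactly one positive patient. Neither is in the documents.
- *The six-level Wagner scale is worse.* The expected-count condition fails there too, but simulation at 3/12, 5/10 and 7/8 splits under two assumed grade distributions gave rejection rates of about 2.5% to 5.2%.
- *The gene-expression results are affected.* The table of variables labels gene expression as qualitative, but it also gives a measuring unit, and the procedure describes relative quantification. The documents do not show that it will be tested as a category.

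The plan also does not tie the Chi-square test to sex in so many words. That link is an inference, though no other grouping is named.

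**Conclusion.** The point holds in a limited form. It is certain from the plan's own numbers that the usual condition for the Chi-square test fails in every 2x2 table by sex, with a smallest expected count of 3.27 at most. It is possible, not certain, that a sex difference will be called significant that Fisher's test would not support. This needs the uncorrected form of the test and one of the 2 to 6 discordant tables at each split. Clear inflation of the error rate, to about 0.09 to 0.10, needs a very uneven split (3/12 or 1/14) and is an assumption about a split the documents do not give.

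The consequence is low. The comparison by sex is descriptive, and the hypothesis and general objective concern change in gene expression. It remains worth correcting because an exact calculation is available from the same counts, and naming it also removes the ambiguity over the continuity correction.

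**What to change.** In the Statistical analysis section, replace the Chi-square test for qualitative variables with one pre-specified exact test: Fisher's exact test (two-sided) for binary characteristics and the Fisher-Freeman-Halton test for Wagner grade. If less conservatism is wanted, state the mid-p version in advance. Choose one only, since mid-p and Fisher differ on tables such as 3/7 versus 0/8 (0.038 against 0.077).

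The cost is one line of text and no new data. If tables have already been produced, the p-values can be recomputed from the same counts. The downside is that Fisher's test is conservative (maximum type I error about 0.035), so fewer descriptive sex differences will be called significant. At a 1/14 split none can be, because the smallest possible p-value is 1 / 15 = 0.067. Frequencies and percentages by sex should be shown whatever the p-value.

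### A Shapiro-Wilk pre-test on 15 patients chooses the test and summary for gene expression; one log-scale within-patient analysis would treat all genes alike and avoid a modest loss of power

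*Combined protocol and SAP*

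**What the plan says.** The Combined protocol and SAP describes a "quasi-experimental, longitudinal, prolective, analytical study" of "15 patients with diabetic foot". The Specific objectives list 11 genes, each measured "in the basal state, at 12 and 30 sessions of treatment in the hyperbaric chamber". Under Elimination, patients can be removed for "Incomplete data for any variable", so the analysed number may be below 15.

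The Statistical analysis section sorts "quantitative variables according to the Shapiro-Wilk normality test, normally distributed variables are presented in means and standard deviation". Variables judged normal are "compared with Student's t-test, those related with ANOVA test". The others are given as medians with interquartile ranges and compared by Mann-Whitney, or by Kruskal-Wallis where the data are related.

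The Procedure section normalises expression to 18s. "Relative quantification (normalization) of gene expression was determined using the" 2-to-the-power-of-CT method, and no log transformation is mentioned. The Operationalization of variables table classes gene expression as qualitative, although the quantification step yields a continuous number.

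The plan does not state the significance level of the pre-test, the unit it is applied to (gene, time point or within-patient change), or what happens when a gene passes at one time and fails at another.

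**The concern.** The hypothesis is about change within patients. The CT difference is the measured quantity, and raising 2 to that power stretches the upper tail. The natural scale is therefore log2. A normality test on the raw scale mostly asks whether a known skew happens to be visible in 15 values.

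Two things are at stake:

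- **Consistency.** Some genes would be reported as means with a parametric test and others as medians with a rank test, partly by chance. The plan's silence on the unit also leaves the analyst a choice after seeing the data.
- **Power.** The study is small. Both branches of the rule are less efficient than a log-scale paired analysis when the data are close to log-normal.

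**Working it through.** **Inputs from the documents.** n = 15, one group, three time points, 11 genes, significance at p<0.05 (two-sided assumed). The sample size comes with no effect size, SD or power, so there is no planned power to reproduce.

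**Assumed inputs.** Log2 expression is normal. Between-patient SD (s_b) and within-patient SD (s_w) are each 0.5 or 1. The pre-test uses the 0.05 level on raw values.

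**Step 1, reference effect.** For a two-sided paired t-test, the noncentrality is d × √n. With d = 0.78 this is 0.78 × √15 = 3.02, against a critical value of 2.145 on 14 degrees of freedom, and power is 80%. The SD of a paired difference is √2 × s_w, so the log2 change is 0.78 × 1.414 × 0.5 = 0.55 or 0.78 × 1.414 × 1 = 1.10. These are fold changes of about 1.5 and 2.1.

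**Step 2, how often the skew is missed.** In simulated samples of 15 log-normal values, Shapiro-Wilk accepts normality about 77%, 41% and 15% of the time at total log2 SDs of 0.5, 1.0 and 1.5.

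**Step 3, disagreement within a gene, if the pre-test is run at each time point.** The three verdicts differ in about 43-66% of genes over the assumed SDs. That is 0.43 × 11 = 4.7 to 0.66 × 11 = 7.3, or about 5 to 7 of the 11. A wider grid (total log2 SD 0.5 to 1.5, within-patient correlation 0 to 0.7) gives 35-73%. Even truly normal raw data give 14-15%.

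**Step 4, cost of the pre-test alone, basal versus session 30.** Correct paired tests are used in both strategies: a log-scale paired t-test, against a pre-test followed by a paired t-test or signed-rank test on raw values.

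- Log-scale paired t-test: about 80%.
- Pre-test at each time point: 71-76%, a loss of 80 − 76 = 4 to 80 − 71 = 9 points.
- Pre-test on the within-patient change: 69-76%, a loss of 4 to 11 points from the rounded figures.

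Allowing for simulation error, the cost is roughly 4 to 10 points, and it does not depend on testing each time point separately. With no true change, the paired pre-test rule rejects 4-6% of the time.

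**Step 5, separating the pre-test from the choice of tests.** This uses the wider grid, with half of the change present by session 12 and 1,000 trials per scenario (error about 1.5 points).

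| Strategy | Power, three time points | Power, basal vs session 30 |
|---|---|---|
| Log-scale within-patient analysis | 68-73% | 78-82% |
| Pre-test, then related-sample tests | 53-63% | 69-79% |
| Pre-test, then independent-sample tests, correlation 0 | 69-74% | 78-82% |
| Same, correlation 0.5 | 34-37% | 50-57% |
| Same, correlation 0.7 | 13-14% | about 30% |

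Scenario by scenario, the pre-test alone costs 2-10 points for basal versus session 30 and 7-15 points over three time points. Treating related data as independent costs far more once values within a patient are correlated: 33-36 points over three time points at correlation 0.5, and 57-58 at 0.7. At correlation 0 there is no such loss.

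**The case against.** **Mixing within a gene is not written into the plan.** Naming ANOVA or Kruskal-Wallis for related data can be read as one overall test per gene. On that reading methods differ between genes but not between times for one gene. If each patient's own basal value is the calibrator, every basal value is 1 and Shapiro-Wilk cannot be run there at all. This stands: the 43-66% is conditional on testing each time point with basal values that vary.

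**The plan's low power might be blamed on the pre-test.** Most of it should not be. The larger loss comes from independent-sample tests on related data. Mann-Whitney may be meant for the comparison by sex, but Kruskal-Wallis is named for related variables, and ANOVA is not specified as repeated-measures. This stands, and it is why the 4 to 10 points are calculated with correct paired tests on both sides.

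**A reader might infer that the pre-test produces excess false positives.** The documents do not support this. In the paired comparison the error rate stays near nominal. Inflation would need a one-sample test of fold change against 1, which the plan never names.

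**A reader might infer that mixed summaries defeat a comparison of the 11 genes.** No objective compares genes with one another, so the harm is inconsistent treatment and reporting.

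**Read literally, the qualitative label sends gene expression to Chi-square, not to the pre-test.** That is a contradiction to resolve, and it does not defend the pre-test.

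**Conclusion.** The concern holds in a limited form. A Shapiro-Wilk test on at most 15 values chooses test and summary for outcomes that have a natural log scale. It can treat genes differently and, depending on an unstated detail, time points of one gene differently. Its own power cost is modest: roughly 4 to 10 points for basal versus session 30, from about 80% to 70-76%, with type I error near nominal.

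Every figure rests on assumed SDs, an assumed effect and roughly log-normal expression, since the documents supply none of these. The direction is well supported; the size would shift with the real variability. The change is worth making because n = 15 leaves little room and because the same edit removes the larger loss from independent-sample tests.

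**What to change.** In the Statistical analysis section:

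- Remove the normality pre-test for gene expression.
- Analyse every gene on the log2 (CT-difference) scale with one pre-specified within-patient analysis: either a repeated-measures model or paired t-tests, for basal versus 12 sessions and basal versus 30 sessions.
- Report the geometric mean fold change with its 95% CI for every gene.
- Keep signed-rank and Friedman tests as a sensitivity analysis, in place of Mann-Whitney and Kruskal-Wallis for the related data.
- Correct the variable type of gene expression in the Operationalization of variables table so that it agrees with the quantitative analysis.

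This changes wording only and needs no new assays or patients. The costs are that results appear as geometric mean fold changes instead of raw means or medians, and that the main analysis relies on roughly log-normal data, which the rank-based sensitivity analysis helps to check.
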